4.5.1 Adverse Events and Serious Adverse Events

All AEs will be reviewed by the Clinical Research Scientist (CRS) or Designee prior to database lock and unblinding and will be coded to a system organ class (SOC) and preferred term (PT) using the Medical Dictionary for Regulatory Activities (MedDRA). During this review stage, AEs will be further categorized as oral or non-oral.

Treatment emergent adverse events (TEAEs) are defined as AEs that occur on or after the first study product use at the Baseline visit (if this date is missing a suitable alternative will be used e.g., date of randomization). AEs with an onset date/time prior to the first study product application will be considered as non-treatment emergent.

The following AE tables and listings will be produced, presented by study product group and overall:

- Table of TEAEs by SOC and PT (Table 14.3.1.1).
- Table of TEAEs by Oral/Non-Oral and PT (Table 14.3.1.2).
- Table of treatment related TEAEs by SOC and PT (Table 14.3.1.3).
- Table of treatment related TEAEs by Oral/Non-Oral and PT (Table 14.3.1.4).
- Table of AEs related to COVID-19 by SOC and PT (Table 14.3.1.5).

3% PVM/MA + 5% KNO₃ Toothpaste
218220

- Listing of all AEs (Listing 16.2.7.1 for all randomized subjects; Listing 16.2.7.2 for non-randomized subjects).
- Listing of all AEs related to COVID-19 (Listing 16.2.7.3 for all screened subjects)
- Listing of deaths (Listing 14.3.2.1).
- Listing of non-fatal SAEs (Listing 14.3.2.2).
- Listing of TEAEs leading to study or product discontinuation (Listing 14.3.2.3).
- Listing of TEAEs classified as Oral (Listing 14.3.2.4)

In the event that there is nothing to report, a null table or listing will be produced. In addition, in case of more than 5 SAEs, a table with SAEs by SOC and PT will be produced.

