## 4 STUDY DESIGN

### 4.1 Overall Design

This will be a PoP, single centre, 8-week, randomised, controlled, examiner blind, parallel design, stratified (by maximum Baseline Schiff sensitivity score of the two selected test teeth) clinical study in healthy subjects with sensitive teeth.

To help minimise the potential impact of 'placebo'/'no treatment' effects, and to standardise oral hygiene practices, an acclimatisation period (2-4 weeks) will be included between the Screening and Baseline assessments. Subjects who meet all study criteria at both Screening and Baseline visits will be randomised to one of the 4 study products.

In line with widely recommended oral hygiene practice and typical consumer habit, study subjects will be requested to brush their teeth for one timed minute twice daily (morning

Property of GSK Consumer Healthcare - Confidential

May not be used, divulged, published or otherwise disclosed without the consent of  
 GSKCH

CCI

Clinical Protocol Template v7.0

Page 23 of 100

and evening) with their assigned study toothpaste, covering the toothbrush head with full ribbon of toothpaste (approximately 1.5 g) on each brushing occasion.

Two independent stimulus-based (tactile and evaporative) measures of tooth sensitivity will be employed.

- A tactile stimulus will be administered using a constant pressure probe (Yeaple Probe (Polson et al., 1980)). Subject response will determine the tactile threshold in grams (g).
- An evaporative (air) stimulus will be administered using a dental air syringe. Subject response will be evaluated using the Schiff sensitivity scale (Schiff et al., 1994).

Sensitivity to tactile and evaporative (air) stimuli will be assessed at Screening (Visit 1) and then at various time points across the 8-week usage period - Baseline (Day 0), Day 3 and Weeks 2, 4 and 8. A single clinical examiner will assess both measures for the duration of the study for all study subjects. On completion of the Baseline assessments, the clinical examiner will select two 'test teeth' from those that qualified at Screening and Baseline, for assessment of tactile and evaporative (air) sensitivity at all subsequent visits. In addition, the remaining 'eligible teeth' identified as sensitive to both tactile and evaporative (air) stimuli at Screening will be assessed for evaporative (air) sensitivity only at Day 3 and Weeks 2, 4 and 8.

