**Events Meeting the AE Definition:**

- Any abnormal laboratory test results (hematology, clinical chemistry, or urinalysis) or other safety assessments (e.g. ECG, radiological scans, vital sign measurements), including those that worsen from Baseline, considered clinically significant in the medical and scientific judgment of the investigator (i.e., not related to progression of the underlying disease).
- Exacerbation of a chronic or intermittent pre-existing condition including either an increase in frequency and/or intensity of the condition.
- New conditions detected or diagnosed after study product administration even though it may have been present before the start of the study.
- Signs, symptoms, or the clinical sequelae of a suspected drug-drug interaction.
- Signs, symptoms, or the clinical sequelae of a suspected overdose of either study product or a concomitant medication. Overdose per se will not be reported as an AE/SAE unless it is an intentional overdose taken with possible suicidal/self-harming intent. Such overdoses should be reported regardless of sequelae.
- "Lack of efficacy" per se will not be reported as an AE. Such instances will be captured in the product performance assessments. However, the signs, symptoms, and/or clinical sequelae resulting from lack of performance will be reported as AE if they fulfill the definition of an AE.

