## **10.6 Follow-up of AEs and SAEs**

After the initial AE/SAE report, the investigator is required to proactively follow up with each subject and provide further information on the subject’s condition.

All AEs (serious and non-serious) will be followed until resolution, until the condition stabilises, until the event is otherwise explained or until the subject is lost to follow-up.

Property of GSK Consumer Healthcare - Confidential

May not be used, divulged, published or otherwise disclosed without the consent of  
GSKCH

CCI

Clinical Protocol Template v7.0

Page 72 of 100

The investigator is obligated to perform or arrange for the conduct of supplemental measurements and/or evaluations as may be indicated or as requested by GSK CH to elucidate as fully as possible the nature and/or causality of the AE. This may include additional laboratory tests or investigations, histopathological examinations, or consultation with other health care professionals.

New or updated information will be recorded on the AE eCRF page and on the SAE form (subject to the classification of the AE).

The investigator will submit any updated SAE data to GSK CH within 24 hours of receipt of the information.

Investigators are not obliged to actively seek AEs in former subjects. However, if the investigator learns of a SAE, including death, at any time after a subject has been discharged from the study, and considers the event reasonably related to study product or study participation, the investigator will promptly notify GSK CH by emailing the information to the GSK CH Clinical Operations Safety Reporting email box **PPD**

**PPD** The GSK CH Study Manager or designee will be responsible for forwarding the information to the Case Management Group, Global Clinical Safety and Pharmacovigilance group mailbox at GSK **PPD**

The investigator will submit any updated SAE data to GSK CH within the designated reporting time frames.

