#### **12.3.3 Safety Analyses**

The Safety population will be used for safety analyses. Safety analyses will be performed according to product received. All AEs will be reviewed by the Clinical Research Scientist, or designee, prior to database lock and unblinding and will be coded using the MedDRA. During this review stage, AEs will be further categorised as oral or non-oral. AEs will be listed and summarised by product received. SAEs will also be listed. AEs will be regarded as 'treatment' emergent if they occur on or after the first product use at the Baseline visit.

Property of GSK Consumer Healthcare - Confidential

May not be used, divulged, published or otherwise disclosed without the consent of  
 GSKCH

CCI

Clinical Protocol Template v7.0

Page 81 of 100

The following AEs tables will be produced, presented by product group:

- listing of all AEs (randomised subjects and non-randomised subjects);
- summary of AEs;
- treatment emergent AEs by Oral/Non-Oral and Preferred Term (PT);
- treatment emergent AEs by System Organ Class (SOC) and PT;
- treatment emergent treatment related AEs by Oral/Non-Oral and PT;
- listing of serious AEs (if there are no SAEs, a null listing will be produced; if there are more than 5 treatment emergent serious AEs (SAEs), a table will be produced in place of the listing by SOC and PT);
- non-serious treatment emergent AEs by SOC and PT (only produced if there are more than 5 SAEs).

The results of the OST and OHT examinations will be listed and the results of the OST examinations will be tabulated.

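### Treatment emergence is set by onset date alone, and no rule covers worsening of an AE already open from the run-in, so such events can be left out of the TEAE displays

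*SAP*

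**What the plan says.** SAP 4.5.1 defines the term by date: "Treatment emergent adverse events (TEAEs) are defined as AEs that occur on or after the first study product use at the Baseline visit". It then adds an explicit exclusion: "AEs with an onset date/time prior to the first study product application will be considered as non-treatment emergent". Protocol 12.3.3 agrees: "AEs will be regarded as 'treatment' emergent if they occur on or after the first product use at the Baseline visit". No clause in either document deals with a change in intensity or seriousness after first use.

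The design includes a run-in: "an acclimatisation period (2-4 weeks) will be included between the Screening and Baseline assessments" (protocol 4.1). AE collection starts at signed consent (protocol 10.3), and the AE definition in protocol 10.1 expressly covers an acclimatisation product. AE records with an onset before Day 0 are therefore expected.

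Two protocol passages bear on worsening. Section 10.1 counts the following as an AE: "Exacerbation of a chronic or intermittent pre-existing condition including either an increase in frequency and/or intensity of the condition". Section 10.6, on follow-up, says: "New or updated information will be recorded on the AE eCRF page".

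SAP 4.5.1 limits Tables 14.3.1.1 to 14.3.1.4 to TEAEs. The oral AE listing (14.3.2.4) is limited in the same way, and so is Listing 14.3.2.3: "Listing of TEAEs leading to study or product discontinuation".

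**The concern.** TEAEs are the only safety endpoint in the objectives tables (protocol Table 3-1, SAP 1.2). By product name and description, the acclimatisation paste and the negative control are the same commercial toothpaste (protocol Table 6-1). At Day 0, therefore, only the three experimental arms change formulation. Suppose a subject has mild oral irritation in the run-in that becomes severe after the switch. That is a tolerability observation the study should count, and one caused by the change of paste could arise only in those three arms.

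Under the stated rule, whether it counts depends on how the site enters it. One site practice would put the event in the TEAE tables and another would keep it out, and neither document chooses between them. The discontinuation listing has the same weakness. SAP 4.5.1 produces a null listing when there is nothing to report, so Listing 14.3.2.3 could be empty while Table 14.1.1 shows a subject who stopped because of an AE.

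**Working it through.** This is a check of the text. The plan gives no figure to reproduce on this point.

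**Step 1: the rule.** From SAP 4.5.1 and protocol 12.3.3, an AE record is a TEAE if its onset is on or after first study product use (Day 0). Otherwise it is not.

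**Step 2: apply the rule to the ways a worsening could be recorded.** The days are illustrative.

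| Case | How it is recorded | Onset day(s) | TEAE? |
|---|---|---|---|
| A | Run-in AE kept as one record and updated when it worsens on day 10 | -7 | No |
| B | Run-in AE record, plus a new record for the worsening | -7 and 10 | Second record: yes |
| C | Condition present before consent; exacerbation entered as an AE | 10 | Yes |

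The loss occurs in case A only.

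**Step 3: which case do the documents require?** Protocol 10.6 sends updated information to the AE page. It does not say whether that means the record already open, nor what happens to the onset date. Protocol 10.1 makes exacerbation of a pre-existing condition an AE, and protocol 9.3.1 makes worsening since the Screening soft-tissue examination an AE. Both fit case B or C, but neither says how to date the worsening of an AE already on file. Cases A and B are both open.

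**Step 4: what case A loses and keeps.**

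- Lost: Tables 14.3.1.1 to 14.3.1.4 and Listings 14.3.2.3 and 14.3.2.4.
- Kept: Listing 16.2.7.1 (all AEs in randomised subjects, a topline output); Listings 14.3.2.1 and 14.3.2.2 if the event is fatal or serious; and the reason for withdrawal in Table 14.1.1 and Listing 16.2.1.1.
- Partly kept: a soft-tissue finding counts in Table 14.3.4.1. That table shows only abnormal, not abnormal or not examined by visit, so a finding that worsens does not change category.

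Apart from the COVID-19 table (14.3.1.5), every AE table in the SAP's list of displays is limited to TEAEs. No summary table would pick up case A.

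**Step 5: size per subject.** About 120 randomised over 4 arms is 120/4 = 30 per arm. One subject is 1/30 = 3.3 percentage points of an arm's TEAE rate. This is the most one omitted subject can change that rate, since a subject with another TEAE is already counted.

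**The case against.** The strongest reply is that the protocol already treats worsening as an AE. If an exacerbation on day 10 is itself an AE under section 10.1, it occurs after first use and is a TEAE under the rule as written. The eCRF completion instructions, which are not among the documents, may say exactly that. This reply stands as far as it goes: it shows that the loss is not inevitable. It does not show that the loss is excluded, because no text requires a new record when an AE on file worsens.

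A reader might infer that protocol 10.6 settles the matter the other way, so that an open AE must keep its run-in onset date and always drops out of the TEAE tables. The text does not support that. It names the AE page without saying which record is meant, and it is silent on the onset date.

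It can also be said that the event is not hidden. It appears in the listings named above, and a reader could find it with about 30 subjects per arm. That is correct, and it limits the harm. A listing does not correct a table of rates, however, and Listing 14.3.2.3 is the display a reader would consult for discontinuations.

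Finally, Baseline repeats the soft-tissue examination and the eligibility review before randomisation (protocol 8.2.1), AE reporting is descriptive, and no decision rule uses TEAE counts. These points reduce the likely number of cases and their consequences. They do not settle how a remaining case is classified.

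**Conclusion.** The point holds as a gap in the definition. Treatment emergence is decided by onset alone, there is no worsening clause, and the recording of worsening in a run-in AE is unspecified. Where such an AE is kept as one record, its worsening on study product, or a withdrawal it causes, is left out of four tables and two listings.

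The documents give no AE rates, so the number of affected subjects cannot be estimated, and any assumed rate of open or worsening events would have no source in them. The supportable figure is about 3.3 percentage points of an arm's TEAE rate per subject, assuming 30 subjects in the arm and no other TEAE in that subject. Efficacy analyses and sample size are unaffected. The correction is worth making because the sole listed safety endpoint should not depend on an unwritten data-entry habit.

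**What to change.** 1. In SAP 4.5.1, define a TEAE as an AE with onset, or with an increase in intensity or seriousness, on or after first study product use. Amend the exclusion sentence to match.
2. State, in the SAP and in the eCRF completion instructions, that such worsening is recorded with its own start date/time and intensity. Without a dated worsening, the new clause cannot be applied.
3. Base Listing 14.3.2.3 on all AEs leading to study or product discontinuation after first study product use, whatever the onset date.

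If step 2 is followed with a separate record, the present onset rule would already capture the worsening. The clause in step 1 is still worth having, because it makes the intention explicit and covers records entered another way.

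Cost: one clause in the SAP, one recording instruction and a changed selection rule for one listing. TEAE counts may rise slightly. The wording of protocol 12.3.3 should be aligned at the next amendment; until then the difference should be noted in SAP Section 5, which at present reports no changes from the protocol.

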### 10.3 Time Period and Frequency for Collecting AE and SAE Information

All AEs, and therefore all SAEs, will be collected immediately after a subject provides consent to participate in the study by the completion (signature) of the ICF until 5 days following last use of the study product (or last procedure).

Medical occurrences that began before obtaining informed consent will be recorded in the Medical History/Current Medical Conditions section of the eCRF not the AE section.

Property of GSK Consumer Healthcare - Confidential

May not be used, divulged, published or otherwise disclosed without the consent of  
 GSKCH

CCI

Clinical Protocol Template v7.0

Page 67 of 100

Details recorded by the subject on a diary or similar document that meet the definition of an AE must also be discussed with the subjects and transcribed in the AE section of the eCRF.

All SAEs will be recorded and reported to the sponsor, or designee, immediately and under no circumstance should this exceed 24 hours. The investigator will submit any updated SAE data to the sponsor within 24 hours of it being available.

Investigators are not obligated to actively seek AEs or SAEs after the conclusion of the study participation. However, if the investigator learns of any SAE, including a death, at any time after a subject has been discharged from the study, and considers the event to be reasonably related to the study product or study participation, the investigator must promptly notify the sponsor.

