3. Evaporative (air) assessment will follow tactile assessment, with minimum 5 minutes between last tactile assessment and first evaporative (air) assessment (to allow tooth recovery).

Visit 1: assess the evaporative (air) sensitivity of teeth with tactile threshold ≤ 20 g.

Visit 2: assess the evaporative (air) sensitivity of all eligible teeth identified at Screening.

Visits 3 to 6: assess the evaporative (air) sensitivity of the two test teeth first, then assess the evaporative (air) sensitivity of all other eligible teeth identified at Screening.

3% PVM/MA + 5% KNO₃ Toothpaste
218220

- 4. Subject will be required to bring their study supplies (minus timer) to every visit.
- 5. Perform visual check of returned study supplies, review diary and evaluate compliance.
- Visit 2:** check compliance with use of acclimatization toothpaste.
- Visits 3 to 6:** check compliance with use of study product.
- Visits 2 to 6:** check compliance with Lifestyle Guidelines/Medication requirements.
- 6. DHEQ must be completed before the NRS question is asked; DHEQ and NRS question must be completed prior to OST examination/clinical assessments.
- DHEQ **Visit 2:** complete all questions
- DHEQ **Visits 3 to 6:** complete Section 1 Q7 to Q9 and Section 2 all questions.
- 7. Record AEs from signing of informed consent until 5 days after last use of study product

3% PVM/MA + 5% KNO₃ Toothpaste
218220

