4.6 Analysis of Other Variables

NA

5 Changes to the Protocol Defined Statistical Analysis Plan

There were no changes or deviations to the originally planned statistical analysis specified in the protocol version 2.0 (Dated: 25/JAN/2022).

3% PVM/MA + 5% KNO₃ Toothpaste
218220

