14.3 Safety Data Summary Tables and Figures

14.3.1 Displays of Adverse Events

	Table	14.3.1.1	Treatment Emergent Adverse Events by System Organ Class and Preferred Term	Safety Population	Table 14.3.1.1	
	Table	14.3.1.2	Treatment Emergent Adverse Events by Oral/Non-Oral and Preferred Term	Safety Population	Table 14.3.1.2	
	Table	14.3.1.3	Treatment Related Treatment Emergent Adverse Events by System Organ Class and Preferred Term	Safety Population	Table 14.3.1.1	
	Table	14.3.1.4	Treatment Related Treatment Emergent	Safety Population	Table 14.3.1.2	

GlaxoSmithKline Consumer Healthcare Confidential

CCI [REDACTED] Statistical Analysis Plan Template v6.0

Page 29 of 34

3% PVM/MA + 5% KNO₃ Toothpaste
218220

CSR Section	TLF	Number	Title	Population	Template	Topline
			Adverse Events by Oral/Non-Oral and Preferred Term			
	Table	14.3.1.5	Adverse Events Related to COVID-19	Safety Population	Table 14.3.1.5	

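### The COVID-19 AE table and the conditional SAE table are not limited to treatment-emergent events, and the SAP's departures from the protocol's serious-event displays are undeclared

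*SAP*

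**What the plan says.** **Collection.** Protocol 10.3 states: "All AEs, and therefore all SAEs, will be collected immediately after a subject provides consent to participate in the study". The schedule footnote in SAP 1.1 gives both ends of the window: "Record AEs from signing of informed consent until 5 days after last use of study product". Consent is taken at Visit 1, before the acclimatisation period.

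**Definition.** SAP 4.5.1 counts an AE as treatment emergent if it occurs on or after first use of study product at Baseline, and classes anything earlier as non-treatment emergent. The stated safety endpoint is treatment emergent adverse events.

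**Tables.** SAP 4.5.1 lists its AE displays as presented by study product group and overall. Tables 14.3.1.1 to 14.3.1.4 are all restricted to TEAEs. The next entry is "Table of AEs related to COVID-19 by SOC and PT (Table 14.3.1.5", with no such restriction. Appendix 1 titles it "Adverse Events Related to COVID-19" and assigns it to the Safety Population.

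**Conditional SAE table.** After the list, SAP 4.5.1 adds that "in case of more than 5 SAEs, a table with SAEs by SOC and PT will be produced". Protocol 12.3.3 instead says that "if there are more than 5 treatment emergent serious AEs (SAEs), a table will be produced in place of the listing". The protocol also plans a conditional by-SOC-and-PT table of non-serious treatment-emergent AEs.

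**Declared changes.** SAP Section 5 states: "There were no changes or deviations to the originally planned statistical analysis specified in the protocol version 2.0".

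**The concern.** A safety table with one column per product is read as a count of events that followed use of that product. During the run-in every subject used the same acclimatisation toothpaste, and randomisation took place only at Visit 2. If a run-in event enters a by-product table, it sits in the column of a product that had not been assigned when the event occurred.

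Two displays are open to this. Table 14.3.1.5 is always produced, as a null table if there is nothing to report. The SAE table appears only if its trigger is met, but that trigger is itself looser than the protocol's.

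Separately, a reader who relies on Section 5 would believe that the SAP reproduces the protocol's safety displays. For the serious-event displays it does not.

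**Working it through.** The documents give no figure for this point, so the check is mainly a comparison of text, followed by a rough guide to size.

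**1. Can a run-in event reach Table 14.3.1.5?**
- AEs are recorded from consent (protocol 10.3), and protocol 10.1 includes events on an acclimatisation product in the definition of an AE.
- The Safety Population is every randomised subject with at least one use of study product (SAP 4.1.3). Such a subject's run-in events stay in the data.
- SAP 4.5 reports all safety data for that population by the product actually received.
- Table 14.3.1.5 covers AEs, not TEAEs, and is in the list presented by study product group.

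So yes, as written. The wording does not look accidental: the same list writes TEAE for four tables and two listings, and AE or SAE elsewhere.

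**2. Can a run-in event reach the SAE table?** The sentence refers to SAEs without a limit, in both trigger and content. It stands outside the list headed as by study product, so its by-product layout follows only from the general rule in SAP 4.5.

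**3. Protocol 12.3.3 against SAP 4.5.1 and Appendix 1**
- Trigger for the SAE table: more than 5 treatment-emergent SAEs in the protocol; more than 5 SAEs in the SAP.
- Role of the table: replaces the SAE listing in the protocol; is added to the listings in the SAP.
- Conditional non-serious TEAE table: planned in the protocol; in neither SAP 4.5.1 nor Appendix 1.
- Conditional SAE table: described in SAP 4.5.1 but not entered in Appendix 1.

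The two triggers can disagree. With 6 SAEs, 1 of them in the run-in, the SAP count is 6 (more than 5, so the table is produced) and the protocol count is 6 − 1 = 5 (not more than 5, so it is not).

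**4. Guide to size**
- Run-in: 14 to 28 days (protocol 4.1).
- Study product use: 56 days nominal, ± 2 days (Schedule of Activities).
- Follow-up after last use: 5 days (protocol 10.3).

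Run-in share of the window = run-in days / (run-in days + days of use + 5).
- Nominal Day 56: 14/(14 + 61) = 14/75 = 18.7%; 28/(28 + 61) = 28/89 = 31.5%.
- Widest range with the visit tolerance: 14/(14 + 63) = 14/77 = 18.2%; 28/(28 + 59) = 28/87 = 32.2%.

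This is a share of time. It is a share of events only if the event rate is constant and every run-in case goes on to be randomised. With about 30 subjects per arm, one misplaced subject moves a column by 1/30 = 3.3 percentage points.

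**The case against.** The strongest reply is that this is a small mismatch of documentation, and that more could be read into it than the text supports. Several points stand.

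- **Content of the SAE table.** A reader might infer that the SAP changed what the table contains. The protocol attaches its treatment-emergent condition to the trigger only, and the listing that the table replaces is not so limited. Only the change of trigger is shown. The protocol is itself loose: its non-serious TEAE table is triggered by more than 5 SAEs, without the qualifier.
- **Conflict with the protocol over COVID-19.** A reader might infer that Table 14.3.1.5 contradicts the protocol. Protocol 12.3.3 plans no COVID-19 table, so there is nothing to contradict. It also plans, by product group, an AE summary and an all-AE listing that are not limited to TEAEs.
- **Purpose.** Table 14.3.1.5 may be meant as a record of pandemic impact, alongside the COVID-19 disposition counts in SAP 4.1.1. Including the run-in would suit that purpose, but it does not make a study-product column the right place for run-in events.
- **Use of product.** A reader might infer that no subject had used the paste under which a run-in event is counted. The acclimatisation product and the negative control are the same commercial toothpaste, so that is literally true only of the other three arms. In all four arms the product had not yet been assigned.
- **Size.** A reader might take 19–31% as the share of misplaced events. Subjects with run-in illness may never be randomised, for instance through the exclusion for antibiotics before Baseline or the COVID-19 non-randomisations counted in SAP 4.1.1. Their events then leave the Safety Population.
- **Table shells.** These are not in the documents, so a restriction imposed there cannot be checked.

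None of this supplies the missing limit in SAP 4.5.1 or makes the Section 5 statement correct.

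**Conclusion.** The point holds and is minor. As written, Table 14.3.1.5 counts a randomised subject's run-in COVID-19 event under a study product assigned later. The conditional SAE table would do the same for SAEs, on the reading that SAP 4.5 governs its layout. The SAP also loosens the protocol's SAE trigger, omits the conditional non-serious TEAE table and leaves the conditional SAE table out of Appendix 1. Section 5's statement of no changes is therefore wrong whether or not any SAE occurs.

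The number of events affected is unknown, because the documents give no AE or SAE rate. The run-in is about 19–31% of the collection window at nominal timing. That is probably an upper guide to the share of events, given the loss of run-in cases before randomisation; early withdrawal after randomisation would push modestly the other way. SAEs are likely to be few in healthy subjects using toothpaste, and the SAE table may never be needed.

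It would be wrong to conclude that the main safety results are affected. Tables 14.3.1.1 to 14.3.1.4 are limited to TEAEs and address the stated endpoint, and no success criterion depends on either table discussed here.

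**What to change.** In SAP 4.5.1, Section 5 and Appendix 1:

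1. Restore the protocol's trigger of more than 5 treatment-emergent SAEs.
2. Limit by-product counts in Table 14.3.1.5 and the SAE table to treatment-emergent events. Alternatively, show run-in events in a separate acclimatisation (pre-treatment) column, which keeps any pandemic-impact purpose. Keep all events in Listings 16.2.7.1 to 16.2.7.3.
3. State that the SAE table is presented by product received.
4. Restore the conditional non-serious TEAE table, state whether its trigger counts all or only treatment-emergent SAEs, and add both conditional tables to Appendix 1. Otherwise, declare and explain the departures in Section 5.

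The cost is a few lines of SAP text, two Appendix 1 entries and a filter on the treatment-emergent flag that the other AE tables already need. No new data are required.
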